Specific Aim 2: Pilot test the 7-week BullyDown primary prevention program for feasibility and acceptability in an RCT of 150 middle adolescents. Youth will be randomly assigned to either BullyDown, a 4-message-per-day program, or an attention-matched control group talking about ‘healthy lifestyle’ topics (e.g., exercise). Our main outcome measures will be feasibility (e.g., recruitment and enrollment rates) and acceptability (e.g., positive program appraisal) at intervention end. The behavioral outcomes we will measure to motivate power analyses for a future R01 include: (1) bullying perpetration, (2) other aggressive behavior directed towards peers, and (3) bystander behavior in the past 30 days at 3-month post-intervention. We also will examine behavioral indicators at intervention end to observe proximal effects.

Given the limited impact of existing school-based interventions and the time associated with implementing them during school time, more efficient and effective intervention methods are needed. Programs that can be delivered to youth in middle adolescence, typically of middle school aged, irrespective of whether they are attending school physically or virtually may be especially relevant as school boundaries become more fluid. BullyDown addresses this critical need by providing a scalable program that could be quickly and cost-effectively disseminated nationally. If efficacious, we will test the intervention in an R01-funded RCT. Future endeavors could include adapting the program for Spanish-speaking youth and dynamically tailoring content to reported bullying behaviors.

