Changed phone numbers. We have found stability of cell phone numbers to be high in [name]'s other text messaging-based programs. We expect the same will be true for BullyDown. In fact, none of the participants in the beta test dropped out because of non-working or changed phone numbers. If participants are non-responsive to program prompts, we will reach out to them via text, email, and telephone. If that is unsuccessful, a member of the research team will visit the school or Club to check on the participant. During the enrollment phase, we will explain to participants the importance of recording the project phone number somewhere convenient for them so they can contact us if they change their cell phone number.

Assertive follow-up. For each data collection period, we will send automated reminders to youth who have not completed the survey via text messaging. We will engage in personalized outreach if the survey is not completed within a week of the initial invitation. If youth are attending brick and mortar school or BCGA Club, we also will schedule in-school and in-Club data collection so that youth have multiple opportunities to complete the survey, especially if they were absent on a particular day. To maximize data, we also will include youth in the 3-month post-intervention survey even if they have missed the intervention end survey.

Specific Aim 1: Finalize BullyDown content.

Updating content to reflect current school interactions and realities (n=60). Current messages focus primarily on in-person scenarios. We will build upon the development work described above by updating the content so that it better reflects online as well as offline peer interactions. To do so, we will conduct FGs to obtain youth voice about their current experiences with peers online. While it is unlikely that schools will remain online indefinitely, technology is continually being infused into classroom exercises and so we anticipate online interactions to persist even in post-Covid-19 school curriculum.

FGs will be stratified to promote a sense of shared experiences. Stratification characteristics may be sex, race/ethnicity, among others. To promote a diversity of experiences, we will purposefully recruit youth with a variety of bullying experiences. More information can be found in Recruitment and Retention.

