FGs will be conducted over multiple days on CiPHR's highly interactive, bulletin board-style, password-protected website. This online data collection space has been fully vetted for acceptability and feasibility among adolescents in [name]'s previous projects with adolescents.⁵¹⁻⁵⁷ We will ask participants to log on 2-3 times per day at their convenience and respond to moderator questions and comments from other participants.

Example questions include: Now that you are going to school online, how has this changed the way you talk with other kids in your class? How does bullying look different now than when you went to school in-person? Share an example of how someone was bullied in class this past week. What did other kids do? What did your teacher do? Questions will be updated to reflect the academic setting when we are in field.

Krueger and Casey⁵⁸ recommend 3-4 FGs per participant category. Online FGs can accommodate more participants, such that they typically include about 20 participants. Because one or two FGs are needed to match a commensurate sample size as in-person FGs, we plan to conduct about three FGs. We expect coding stability and theoretical saturation, the point at which emerging ideas are repetitive and do not substantively alter the themes developed from initial interviews, to be achieved after the two FGs. If saturation has not occurred, we will conduct additional FGs.

Please see **Data Analysis** for more information.

We will monitor the Boards closely for inappropriate behavior but anticipate that the online format will facilitate the feeling of a safe place and ability to be open and honest about one's experiences.

[name] will review the current content and identify opportunities to update it based upon the FG data. We anticipate examples and scenarios will be expanded to refer to online interactions more directly. To remain within the 4 message per day frequency, an additional week of messaging may be added, based upon how many messages can be simply adapted versus added. Once a draft is ready, [name] will review and provide feedback. [name] will integrate the feedback and then send the revised content back to [name] for review. This process will be iterative until they agree that the relevant themes have been well integrated.

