Data collection. Measures will be collected online at baseline, intervention end, and 3 months post-intervention end. All participants, regardless of study condition, will complete assessments at each time point. Youth will be able to complete the surveys on their own (e.g., at home). If they are attending the brick and mortar school or Club, they also will be able to complete the survey at school or Club in the computer lab if they would prefer. To facilitate self-completion, youth will receive an invitation text message with a unique URL to access the survey. This allows participants to complete the survey at a time and place convenient for them. Alternatively, they can sign up for one of the survey sessions at school or Club that the research staff will schedule with the school or Club administration. To avoid unintentional influence that school and Club staff may have on youth survey answers, only research staff will be present in the computer lab during survey administration.

3D. MEASUREMENTS AND STUDY INSTRUMENTS

Most of the proposed measures below were used in the beta test, suggesting the survey length can be feasibly completed by adolescents in middle school or between the ages of 12-14 year of age. Measures are as follows:

Table 3. BullyDown assessment measures		
Main Outcome measures (intervention end)	Acceptability	We will measure intervention acceptability and tolerability ⁶⁷ with a combination of open-ended questions (e.g., “What aspect of the program did you like the least?”) and questions that form a scale of intervention acceptability (e.g., I liked my Text Buddy; $\alpha = .87$). Participants will estimate the number of messages they received in the past week and percent that they read. The program will record the number of weekly level-up questions answered, and the number answered correctly, as well as the number of Text Buddy and Forever Friend messages sent.
	Feasibility	We will monitor the number of eligible/ineligible youth, the number of parental permission forms received, the number of youth invited but who decline to take part, and the retention rate.

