validated survey question has been used successfully in [name] up with Media survey, which included youth as young as 10 years old.⁷⁸ 4) **Exposure to community violence:** Four JVQ questions will measure exposure to community violence (e.g., Have you ever seen someone get attacked or hit on purpose?).⁷⁷ 5) **Alcohol use:** We will use the YRBS question to measure alcohol use in the past year and in the past 30 days.⁷⁹ 6) **Literacy** will be measured with the Comprehension subscale of the Stanford Diagnostic Reading Test⁸⁰. It was designed to be used by students with low literacy and has high internal validity ($\alpha = .84-.90$)⁸¹. And 7) **Demographic characteristics:** Sex assigned at birth, gender identity, sexual identity, age, grade, cell phone number, and number of people living in the home; length of time using text messaging, length of time with current cell phone number, and average text messaging frequency. **Data analysis is described in Statistical Design and Power.**

The reliance on youth self-report bears discussion. We have carefully considered the potential benefits and drawbacks of including teacher report. We decided not to because middle adolescents, those who are 12-14 years of age and typically in middle school, teachers see their students for one class a day. They are unlikely to know everything that occurs during a student's day and whether they are bullying or being bullied in other classrooms. We decided not to collect parent report because parents rarely know about their child's bullying behavior.⁸²

Scientific rigor of the experimental design, methods, and analyses. The rigor of the proposed study is high. For example, random assignment eliminates the possibility of youth being purposefully assigned to a particular study arm. The attention-matched control will reduce the likelihood that behavior change, if detected, is due to the 'attention' youth received by the daily text messages. Program fidelity will be high as the sending of messages is automated and the same for each student.

3E. STATISTICAL DESIGN AND POWER

Specific Aim 1: Finalize the BullyDown program.

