Monitoring of Text Buddy Communication. Text Buddies are paired intervention participants who will be encouraged to text message each other about to discuss program content throughout the intervention. For example: “Talking about your bullying experiences with friends can be hard. Now that you’re equipped with mad communication skills, try talking with your Buddy about the most recent time you saw someone bullied. What did you do? How did you feel? Text your Buddy and share.”

Buddies will be paired based on sex and school / setting so that they will be at different schools / settings based upon findings from the earlier beta test. The software program will identify youth who match on these criteria and automatically pair them. Those who are not automatically paired will be flagged so that the research team can manually pair youth.

We posit that social support from a Text Buddy will positively influence youth over time. However, balancing this with the privacy needs of our participants, who likely do not want to exchange contact information with a stranger, is important. As such, all Text Buddy messages are routed through the study server, replacing the need for this exchange. Participant cell phone numbers will never be distributed to other participants. To send a message, participants will simply text the dedicated BuddyLine, the program phone number that participants will use to communicate with their Buddy. This message is sent directly to the program server, which identifies the intended recipient, and routes the message to the assigned Text Buddy. This methodology will also allow us to measure the amount of interaction between Buddies accurately; if participants texted each other directly, we would have to rely on self-report to measure frequency of contact. For analysis, we will keep a count record to reflect the number of messages sent by each participant.

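### Programme messages received and percent read rest on one past-week recall item, which covers at most one of seven programme weeks and none for youth who answer 7 or more days after the last message (minor)

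*Combined protocol and SAP*

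**What the plan says.** Section 3D, Table 3 places the item in the acceptability row of the main outcome measures, timed at intervention end: "Participants will estimate the number of messages they received in the past week and percent that they read". The same row says the software will record weekly level-up questions answered and answered correctly, and the Text Buddy and Forever Friend messages sent. It does not list programme messages sent or delivered, and no other section names a log of them as a measure.

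The trial has three surveys: "Measures will be collected online at baseline, intervention end, and 3 months post-intervention end". Weekly questions by text message are described in section 3C only for the optional beta test.

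On late completion, section 3C (Assertive follow-up) says: "We will engage in personalized outreach if the survey is not completed within a week of the initial invitation". No closing date is given. Youth who miss the intervention-end survey are still invited to the 3-month survey.

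On message counts, section 4.b (Monitoring of Text Buddy Communication) explains that routing Buddy messages through the server makes the count accurate, whereas "if participants texted each other directly, we would have to rely on self-report to measure frequency of contact". The platform description in section 4.b says the system sends and receives texts through a gateway service.

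On fidelity, section 3D says: "Program fidelity will be high as the sending of messages is automated and the same for each student".

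**The concern.** The recall window is tied to the calendar and not to the programme. A youth who answers promptly describes only the final week. A youth who answers late enough describes a week in which the programme sent nothing: the truthful count is then 0, and percent read is undefined. Better follow-up of slow responders would add more such records, and slow responders may well be the less engaged youth. Those who miss this survey have no record of receipt at all.

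Three uses are at stake:

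- **Reported exposure.** Messages received and percent read are reported as part of a main outcome measure in a pilot meant to inform a larger trial.
- **Engagement analysis.** Section 3E will look for greater intervention impact among more engaged youth. Message exposure is a natural variable there, and false zeros would distort it.
- **Attention matching.** The control arm is meant to receive the same attention. Text Buddies are paired intervention participants, so Buddy counts cannot check this. Programme message counts could.

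The fidelity statement in section 3D concerns sending, so it does not show receipt. The plan also prefers server counts to self-report for Buddy messages, yet uses self-report for the programme's own messages.

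**Working it through.** The plan gives no figure for this item to reproduce. The check is how far the past-week window overlaps the programme.

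**Inputs**
- Programme length: 7 weeks (section 2, Specific Aim 2: "Pilot test the 7-week BullyDown primary prevention program for feasibility and acceptability").
- Possible extension to 8 weeks (section 3C, Updating content: "an additional week of messaging may be added").
- Frequency: 4 messages a day (section 2, Specific Aim 2).
- Recall window: 7 days (section 3D, Table 3).
- d = days from the last programme day to survey completion. The documents do not give its distribution.

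**Formulas**
- Programme days covered = max(0, 7 − d).
- Messages covered = 4 × days covered.
- Share covered = days covered / (7 × programme weeks).

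**Totals**
- 7 weeks: 7 × 7 = 49 days; 4 × 49 = 196 messages.
- 8 weeks: 7 × 8 = 56 days; 4 × 56 = 224 messages.

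**Results**

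| d (days) | Days covered | Messages covered | Share, 7 weeks | Share, 8 weeks |
|---|---|---|---|---|
| 0 | 7 | 28 | 14.3% | 12.5% |
| 1 | 6 | 24 | 12.2% | 10.7% |
| 3 | 4 | 16 | 8.2% | 7.1% |
| 6 | 1 | 4 | 2.0% | 1.8% |
| 7 or more | 0 | 0 | 0% | 0% |

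The best case therefore needs an answer on the last programme day itself.

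**Link to the follow-up rule.** Delay in the table runs from the last message, while outreach in section 3C runs from the invitation. If the invitation goes out on or after the last programme day, anyone who completes only after the one-week outreach point has d of at least 7 and an empty window. If it goes out k days earlier, the window is empty from day 7 + k after invitation. The documents do not give k, so the share of youth affected cannot be derived.

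**Link to the decision rules.** Section 3E judges acceptability by an average of 4 or more on 5-point Likert scales. It judges feasibility by 75% assent and 80% completion at 3 months. Neither uses messages received or percent read.

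**The case against.** The strongest reply is that nothing decisive depends on this item. That stands: the pass/fail rules in section 3E do not use it, and no named analysis does.

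A reader might infer that the plan has no other evidence on exposure and would miss falling use in weeks 1 to 6. The documents do not support this. Table 3 includes software-recorded weekly level-up answers and counts of Text Buddy and Forever Friend messages. Section 3C adds outreach to youth who stop responding to prompts, and content-specific exposure questions at intervention end. Recall is the only stated measure only in the narrow sense of programme messages received and read.

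A reader might also want to put a number on false zeros. If an assumed 10% to 30% of the 76 intervention youth answered too late, that would be 0.10 × 76 ≈ 8 to 0.30 × 76 ≈ 23 records. Nothing in the documents supports that rate, so it is illustration only.

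Table 3 is also a summary and may not give the item verbatim; the survey itself may anchor the question to the programme. That is fair, and the finding is limited to the text as written. A short recall window is reasonable at ages 12 to 14, but that argues for one week of recall, not for the calendar week before the survey.

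Finally, the platform may already hold logs that could be extracted later, so data need not be lost. That lowers the stakes, but the plan does not commit to using them.

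**Conclusion.** The point holds as a minor one. As written, the item describes at most one of seven programme weeks (14.3% of messages), or one of eight (12.5%), less with each day of delay, and nothing from 7 days after the last message. This rests on three assumptions: Table 3 reflects the item's wording, youth answer it literally, and messages go out at 4 a day throughout.

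The effect is confined to the reported message exposure and percent read, any use of them in the engagement analysis, and any check of equal attention between arms. It would be tempting to conclude that the acceptability outcome itself is compromised because the item sits in that row of Table 3. The documents do not support that, since the Likert criterion is separate. The number of youth with an empty window is unknown.

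**What to change.** In Table 3, replace the self-estimated count with the number of programme messages sent to each youth in each week, in both arms, taken from the platform log. Add delivery failures where the gateway returns them; the documents do not say whether it does. Keep self-report only for percent read, worded as *during the last week you were getting program messages*.

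State that percent read still describes only the final programme week, and read it alongside the weekly level-up counts. The log would cover all 49 programme days (56 with an eighth week), and would include youth who miss the intervention-end survey. It would not measure reading in the earlier weeks.

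The cost is one reworded item and one export, with no added survey. The small downside is slightly longer recall for late responders.

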Preliminary behavioral outcome measures (Intervention end and 3-month follow-up)	Bullying perpetration	Bullying will be queried by type (e.g., relational, physical), mode (e.g., online, in-person), and place (e.g., at home, at school). ⁶⁸ Youth who endorse any question at a frequency of 3 times or more in the past 30 days (to reflect repetitive behavior) will be coded as engaging in bullying.
	Other aggression	Youth who report engaging in the above bullying perpetration items, but less frequently so, will be coded as engaging in aggressive acts. ⁶⁸
	Bystander behavior	Youth will be asked if, in the past 30 days, they have seen or heard about (e.g., as a rumor) someone being bullied. Those who say yes will be asked what they did in response. Options will include: nothing, telling an adult, talking to the victim, and standing up to the bully.

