Exogenous variables include: 1) **SEL components:** Communication – youth will be presented with four different scenarios and asked to identify whether it reflects passive, aggressive, or assertive communication. Causey & Dubow's Self-report Coping Measure will be used to measure stress coping and problem-solving. Both are 8-item subscales with acceptable reliability ($\alpha = 0.84$ and $\alpha = 0.84$, respectively). Problem-solving asks youth how often they, for example, “Change something so things will work out.” Empathy will be assessed with the 5-item Empathy subscale in the Teen Conflict Scale ($\alpha = .62$).⁶⁹ Respect for diversity will be measured with the 4-item Support for Cultural Pluralism subscale of the Inventory of School Climate ($\alpha = 0.68$).⁷⁰ Identifying bullying will be measured by showing participants various “features” and asking them to identify those that reflect bullying (i.e., repetitive, with differential power, intent) Attitudes towards bullying and aggression will be measured with the 4-item University of Illinois Positive Attitudes toward Bullying Scale ($\alpha = 0.81$).⁷¹ Bystanders’ intentions will be measured with the 5-item University of Illinois Willingness to Intervene scale ($\alpha = .62$).⁷² Anger and hostility will be measured with the University of Illinois Anger Scale ($\alpha = .81$; e.g., “I got in a physical fight because I was angry”).⁷³ Hostility will be measured with the Symptom Checklist-90 subscale, which is a 6-item scale ($\alpha = .87$).⁷⁴ Impulsivity will be measured with the 4-item Impulsivity subscale from the Teen Conflict Survey ($\alpha = .62$).^{75,76} 2) **Peer victimization:** Victimization questions that mirror the bullying questions described will be asked of all youth. Those who say they have been victimized in at least one way 3 or more times in the past 30 days, by someone with more power than them, will be coded as being bullied. Those who report less frequent victimization and/or an aggressor with equal power will be coded as a victim of other aggressive acts. 3) **Exposure to domestic violence** will be measured using an item from the Juvenile Victimization Questionnaire (JVQ).⁷⁷ This well-

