Transcripts of the FGs will be entered into Dedoose (formerly EthnoNotes),⁸⁵ a mixed methods analysis program. Codes will be generated based on the first FG, reexamined, and refined through constant comparison with the second FG.⁸⁶ A codebook will be created with codes, brief descriptions, and illustrative quotations.⁸⁷ Codes will be both generated inductively and derived from our initial research questions (e.g., how youth interact with their peers and their teacher online). [name] project coordinator and [name] graduate research assistant will code both FGs. To assure inter-coder reliability, we will calculate a kappa value and accept a minimum of 0.75 as the criterion for adequate agreement between coders.⁸⁸ After coding is complete, we will extract themes using an iterative process to highlight evidence contradictory to our conclusions as well as the modal response.⁸⁹ The analysis will result in a report that describes the findings and advises how to integrate them into program content.

Specific Aim 2: Pilot test the 7-week BullyDown intervention for feasibility and acceptability in an RCT of 150 adolescents either in middle school and/or 12-14 years of age.

The **feasibility** of the BullyDown intervention will be determined by our recruitment and retention rates. If at least 75% of eligible studies assent and 80% complete the survey at 3-months post-intervention, we will deem these data points as supportive of a hypothesis of feasibility.

The **acceptability** of program features (e.g., badges, Text Buddy) will be measured using 5-point Likert scales; average scores of 4 or more will be supportive of acceptability.⁹⁰ Youth engagement with the program will be examined to identify potential trends in greater intervention impact (e.g., for those who use the Text Buddy feature).

Post-intervention one-on-one interviews to illuminate the intervention experience will be analyzed using a thematic approach,⁹¹ as our aim will be more descriptive in nature, with a lower level of interpretation needed than is afforded by grounded theory or other qualitative analytical techniques.⁹²

Analyses examining **behavioral outcomes** will be primarily intended to inform power analyses for the larger R01. Data will be treated as intention-to-treat and complete case. We will conduct sensitivity analyses (e.g., missing = bullying behavior) to understand how this may affect our findings. Missing data that are not the main outcomes will be imputed.

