Baseline covariates will be examined to determine whether randomization performed as intended. Any that are significantly imbalanced across study arms will be included in multivariate analyses.

We will use logistic regression to analyze outcomes (e.g., bullying perpetration, other aggressive behaviors; bystander behavior). Once gross estimates of intervention effect have been calculated, covariates will be added to examine

whether they appear to mediate the relation between group assignment and the outcome. Three conditions must be met in order to claim that mediation is present:⁹³⁻⁹⁵ (1) a predictor (e.g., experimental arm) is significantly associated with a mediator (e.g., TPP motivation); (2) The mediator is significantly associated with an outcome (e.g., pregnancy); and (3) when one controls for the mediator, the effect of the predictor on the outcome becomes non-significant. If this effect retains significant but is attenuated, partial mediation is indicated. A 10% or greater change in the point estimate will be deemed clinically significant.^{96,97}

Sex as a biological variable. It is possible that males will respond to the program differently than females because it feels more individual and perhaps, in this way, will resonate more with males.⁸³ Conversely, perhaps because females text message at a greater volume than males,^{36,84} the format of this program may resonate more with them. As such, sex will be explicitly examined as a potential moderator. To understand whether the intervention impact varies by sex, we will test an interaction term, i.e., experimental group X sex. If the term is statistically significant, then it will suggest that boys and girls are impacted differentially by the intervention.

To examine whether/how the intervention effect attenuates over time, we will use generalized estimation equations to analyze the data across follow-up periods using an identity link and exchangeable correlation structure. By entering an interaction term for experimental group X time, we can determine if the intervention is differently impactful at intervention end versus 3-months post-intervention.

Should [name] need statistical guidance, we will take advantage of [name] access to the biostatistics 'core' at the University of North Carolina (please see Budget Justification).

Power analysis

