Because the behavioral outcomes data in this R21 will be used to inform the power analyses of the future R01, we respectfully suggest that a power analysis for this study is premature.

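### Other aggression is the band just below bullying on the same items; if youth coded as bullying are non-events or excluded (the plan does not say), its odds ratio is not a dependable planning input for the R01

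*Combined protocol and SAP*

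**What the plan says.** Section 3D, Table 3, codes as bullying "Youth who endorse any question at a frequency of 3 times or more in the past 30 days". The next row, other aggression, reads "Youth who report engaging in the above bullying perpetration items, but less frequently so, will be coded as engaging in aggressive acts". On the plain reading these are adjacent bands of one frequency scale.

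Specific Aim 2 (section 2) lists the behavioral outcomes as "1) bullying perpetration, (2) other aggressive behavior directed towards peers, and (3) bystander behavior in the past 30 days at 3-month post-intervention". Section 3E gives the model: "We will use logistic regression to analyze outcomes (e.g., bullying perpetration, other aggressive behaviors; bystander behavior". The Power analysis paragraph gives the purpose: "Because the behavioral outcomes data in this R21 will be used to inform the power analyses of the future R01".

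Neither section says how a youth coded as bullying enters the other-aggression model. The peer victimization coding in section 3D is similarly banded ("Those who report less frequent victimization and/or an aggressor with equal power will be coded as a victim of other aggressive acts") and does not settle it. The wording also leaves open a youth with one item at three or more times and another at a lower frequency, who could be coded as both. The source cited for the coding was not available for this review.

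On missing data, section 3E adds "We will conduct sensitivity analyses (e.g., missing = bullying behavior) to understand how this may affect our findings".

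**The concern.** A middle band gains youth from above when they improve and loses them upward when they worsen. If bullying youth are non-events or excluded, a youth who drops from bullying to occasional aggression becomes a new event, and one who escalates to bullying stops being an event. The OR then mixes movement across the upper boundary with movement across the lower one, and the two can cancel or reverse. Exclusion has a further cost: it removes youth on the basis of a post-randomization outcome.

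What is at stake is a planning estimate. This is the second of three behavioral outcomes collected mainly to support power calculations for the R01, and its OR read alone could suggest the wrong effect size or the wrong direction.

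**Working it through.** The plan states no power, alpha, effect size or expected rate for this outcome, so there is no figure to reproduce.

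**Inputs.** Control bullying is set at 22%, the midpoint of the 20-24% in section 1. That figure is per semester, so using it for a 30-day definition is an assumption. The beta-test baseline in section 2 is close: (3 + 2)/22 = 23%. The 30% middle band (range 15-45%) and all movement and loss rates are assumptions.

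**Formulas.** With bullying b, other aggression m and none z (b + m + z = 1), each OR is intervention over control for these odds:
- bullying: b/(1−b)
- other aggression, bullies as non-events: m/(1−m)
- other aggression, bullies excluded: m/z
- any aggression: (b+m)/z

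Control (b, m, z) = (0.22, 0.30, 0.48).

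**1. Step-down.** Half of bullies move to the middle band: intervention (0.11, 0.41, 0.48).
- Bullying: (0.11/0.89)/(0.22/0.78) = 0.44
- Other, non-event: (0.41/0.59)/(0.30/0.70) = 1.62 (1.49-2.10 over the ranges)
- Other, excluded: (0.41/0.48)/(0.30/0.48) = 1.37 (1.22-1.80)
- Any aggression: 1.00

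The reversal ends once enough lower-level aggressors also stop. Non-event: 0.11/0.30 = 37%. Excluded: (0.41−0.30x)/(0.48+0.30x) = 0.625 gives x = 0.11/0.4875 = 23%.

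**2. Escalation.** 20% of the middle band moves up: intervention (0.28, 0.24, 0.48).
- Bullying: (0.28/0.72)/(0.22/0.78) = 1.38
- Other, non-event: (0.24/0.76)/(0.30/0.70) = 0.74
- Other, excluded: 0.24/0.30 = 0.80
- Any aggression: 1.00

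**3. Mixed benefit.** A quarter of bullies step down, a quarter stop, and 20% of the middle band stops: intervention (0.11, 0.295, 0.595). Bullying OR is 0.44 and any-aggression OR 0.63, but other-aggression OR is 0.98 (non-event) or 0.79 (excluded).

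**4. Uniform shift.** Both cumulative odds are halved. Bullying: 0.282 to 0.141, so b = 0.1236. Any: 1.083 to 0.542, so b + m = 0.3514. Intervention is (0.1236, 0.2278, 0.6486).
- Other, non-event: (0.2278/0.7722)/(0.30/0.70) = 0.69 (0.64-0.78)
- Other, excluded: (0.2278/0.6486)/(0.30/0.48) = 0.56 (0.56-0.57)

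Direction is kept over the assumed 15-45% middle band. It need not be outside it: with control (0.24, 0.65, 0.11) the intervention split is (0.1364, 0.6654, 0.1982), and the non-event OR is (0.6654/0.3346)/(0.65/0.35) = 1.07.

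For scale, assuming 80% power, two-sided 5% and the pooled two-proportion formula, the central uniform-shift case needs per arm 584 on the middle band as non-event (0.30 vs 0.228), 220 analyzed with bullies excluded (0.385 vs 0.260), 135 on any aggression (0.52 vs 0.351) and 240 on bullying (0.22 vs 0.124).

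**5. Bullies also coded 1.** If all are, the outcome is any aggression: 1.00 in case 1 and 0.50 in case 4. If half are (control 0.41), case 1 gives (0.465/0.535)/(0.41/0.59) = 1.25, and case 4 gives 0.59.

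**6. Missing set to bullying.** No true effect, assumed loss 24% intervention and 16% control.
- Bullying: 0.24 + 0.76×0.22 = 0.4072 vs 0.16 + 0.84×0.22 = 0.3448, OR 1.31
- Other, non-event: 0.76×0.30 = 0.228 vs 0.84×0.30 = 0.252, OR 0.88
- Other, excluded: 0.228/0.3648 = 0.252/0.4032, OR 1.00
- Any aggression: 0.6352 vs 0.5968, OR 1.18

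**The case against.** The strongest reply is that the outcome is meant to capture aggression below the repetition threshold. Nothing in the plan presents it as total aggression, so it is unfair to fault it for not measuring that. This stands in part. The distinction is legitimate as description, and it is a reason to keep named outcome (2). It does not rescue the stand-alone OR as a planning input.

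The reversal also depends on assumed movement. In case 1 no lower-level aggressor changes, and the mixed case shows attenuation. That is right, so a reader who infers that the OR generally points the wrong way goes too far: the documents give no movement rates, and a uniform shift keeps the direction over the assumed range.

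Nor do the documents say that the R01 will be sized on this OR alone. Bullying is listed first, and if the bands are exclusive and both are reported by arm, the three-way split can be rebuilt.

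Pilot noise is large too. With about 60 per arm (80% of 150, halved) and a 30% event rate, the 95% limits lie a factor of exp(1.96×√(2/(60×0.3×0.7))) ≈ 2.2 either side of the OR. Any R01 size drawn from it would be fragile under either definition. This limits the weight of 584 against 135, but it does not remove the ambiguity in what is being estimated.

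**Conclusion.** The concern holds conditionally. If youth coded as bullying are non-events or excluded, the other-aggression OR is not a dependable planning input: on the central split it is 1.62 or 1.37 when bullying falls by half through step-down, and 0.74 or 0.80 when bullying rises through escalation. If every bullying youth is also coded 1, the problem disappears; if only some are, it shrinks. The sign change under pure step-down or escalation follows from the definition. Its size rests on the assumed split and movement rates.

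Two stronger readings are not supported. A reader might infer that setting missing to bullying always pushes the two outcomes in opposite directions. That holds for non-event coding only (1.31 against 0.88). Under exclusion the OR stays at 1.00, so the rule tests nothing for other aggression. Section 3E offers the rule only as an example and does not say that it applies to this outcome. A reader might also infer that outcome (2) must be dropped, but adding an outcome and a table is enough.

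This is a modest but worthwhile correction to one preliminary estimate. Feasibility, acceptability and the bullying outcome are untouched.

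**What to change.** - State in Table 3 or section 3E how youth coded as bullying are counted in the other-aggression outcome.
- Add any peer aggression (at least once in 30 days, bullying-level acts included) as a binary outcome read beside bullying.
- Report the three-way split (none, other aggression, bullying) by arm at each time point.
- Keep the middle band as a descriptive result, and do not size the R01 on its OR alone.
- If missing is set to bullying, count missing youth as events on both bullying and any aggression. Both then move the same way (1.31 and 1.18 in the example).

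The cost is a recode of items already collected, a sentence or two of text and one more outcome to report. No new survey items are needed. Any aggression alone is blind to moves between the two bands (OR 1.00 in cases 1 and 2), so it must be read with bullying and the three-way table.
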